Dose(s) and Route of Administration	
Route of Administration: Administrations of Tc 99m tilmanocept will occur through an intravenous (IV) and subcutaneous (SC) route of injection.
 
For the IV doses, a single syringe will be used and injected as a slow push into the peripheral venous catheter. The preferred site of catheter placement will be the left or right antecubital vein. At the completion of the injection, a 10 cc sterile normal saline flush will be administered.
 
For SC doses, two syringes will be used and injected bilaterally as a slow push into the ankle(s) or the dorsal surface of the foot (feet).
 
Doses: Cohort 1 subjects will receive an IV administration of 100 µg/ 5 mCi Tc 99m tilmanocept. Cohort 2 subjects will receive an IV administration of 100 µg/ 10 mCi Tc 99m tilmanocept. Cohort 3 subjects will receive a SC and an IV administration of 200 µg/ 5 mCi Tc 99m tilmanocept approximately one week apart.

Study Objectives	
Primary Objective(s):
 
To determine the safety of escalating doses of Tc 99m tilmanocept in HIV subjects with biopsy-confirmed KS.
 
Secondary Objective(s):
 
Concordance between clinical assessment/diagnosis and the localization of Tc 99m tilmanocept by planar and/or SPECT (single photon emission computed tomography)/CT (X-ray computed tomography) imaging in cutaneous and non-cutaneous sites of KS.Qualify and quantify Tc 99m tilmanocept localization intensity on imaging with CD206 locale and quantity by histology and immunohistochemistry (IHC) in biopsied KS lesions to determine optimal IV dose.Concordance of localization of Tc 99m tilmanocept via IV and SC routes of administration by planar and/or SPECT/CT imaging in cutaneous and non-cutaneous sites of KS. 
Exploratory Objective(s):

	
Quantify HHV8 in biopsied KS lesions by real-time polymerase chain reaction (qPCR) 
Safety:
 
General safety will be evaluated by examining the incidence of adverse events (AEs) and changes over time in laboratory tests, vital signs, ECGs (electrocardiogram) and physical examination findings.

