5.3 Treatment Assignment

In this prospective, single center, open-label, non-randomized, dose-escalation, comparative, safety study, Cohort 1 subjects will receive an IV administration of 100 μ g/ 5 mCi Tc 99m tilmanocept. Cohort 2 subjects will receive an IV administration of 100 μ g/ 10 mCi Tc 99m tilmanocept. Cohort 3 subjects will receive a SC and an IV administration of 200 μ g/ 5 mCi Tc 99m tilmanocept approximately one week apart. Cohort 1 will be the starting dose group. Four subjects will be enrolled into Cohort 1.

If one of the four Cohort 1 subjects experiences a noxious pharmacologic activity/an ADR, two more subjects will be treated at the same tilmanocept mass dose and same radiolabel level as the subject with the ADR. If 2 out of 4 or 3 out of 6 subjects experiences a noxious pharmacologic activity/an ADR in

Cohort 1, the maximum tolerated dose (MTD) cannot be determined. If no additional noxious pharmacologic activities/ADRs are observed in the expanded cohort, the dose escalation will continue with Cohort 2. If one additional noxious pharmacologic activity/ADR is observed, the current dose will be deemed the MTD. If more than one additional pharmacologic activity or ADR is observed in the expanded cohort, the previous dose will be deemed the MTD.

If no noxious pharmacologic activities/ADRs are experienced in Cohort 1, Cohort 2 will be open for enrollment.

Dose escalation will continue until the MTD is found or until Cohort 3 is reached with only one ADR or without any ADRs. The maximum tolerated dose is defined as the highest dose level at which no more than 33% of subjects experienced an ADR. Visual representation of the dose escalation scheme may be found in Appendix 2.

NOTE: Adverse Drug Reaction

An Adverse Drug Reaction (ADR) includes all noxious and unintended responses to a medicinal product related to any dose or dose regimen. The phrase “responses to a medicinal product” means that a casual relationship between a medicinal product and an adverse event is at least a reasonable possibility, i.e. the relationship cannot be ruled out.

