9 STATISTICAL METHODS

The study is a prospective, open-label, single-center, dose escalation, comparative, safety study of injected Tc 99m tilmanocept in the detection of and assessment of localization to cutaneous KS or non-cutaneous focus (visceral or other, e.g. CNS [central nervous system]) in HIV-positive subjects with active KS by planar and SPECT/CT imaging. The dose escalation portion of the study is a 4+2 design with no dose de-escalation. The statistical objective of the study is to determine the maximum tolerated dose (MTD) of Tc 99m tilmanocept and to compare the capabilities of Tc 99m tilmanocept to localize in cutaneous and non-cutaneous sites of KS. A study center is defined as a treatment administration site or cohort of treatment administration sites under the control and supervision of the same PI.

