9.4 Sample Size Justification

The dose escalation portion of this study is a design with no dose de-escalation. The sequential cohort enrollment characteristics of this design do not allow a fixed computation of sample size. In a previous study with subjects receiving a 200 µg dose radiolabeled at 5 mCi (i.e., the maximum dose planned for this study), zero (0) subjects had an ADR. Therefore, it is expected that no subjects will have an ADR in this study and that each cohort will enroll the planned sample size of subjects. With 2 cohorts of 4 subjects and one cohort of up to 6 subject, it is anticipated that the study will enroll up to n=14 subjects.

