1.3 Sample Size

The dose escalation portion of this study is a design with no dose de-escalation. The sequential cohort enrollment characteristics of this design do not allow a fixed computation of sample size. In a previous study with subjects receiving a 400 µg dose radiolabeled at 10 mCi (i.e., twice the maximum dose planned for this study), zero (0) subjects had an Adverse Drug Reaction (ADR). Therefore, it is expected that no subjects will have an ADR in this study and that each cohort will enroll the minimum planned sample size of subjects. With 2 cohorts of 4 subjects and one cohort of up to 6 subjects, it is anticipated that the study will enroll no more than n=14 subjects.

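### The plan does not say how dose level is ranked, although Cohort 2 is highest in activity and Cohort 3 in mass, so the stated maximum and the MTD after an ADR-free trial have no defined basis

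*Protocol*

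**What the plan says.** The protocol synopsis and section 5.3 set one dose pair for each cohort. The starting cohort is given 100 µg/5 mCi IV. The second step raises only the radioactivity: "Cohort 2 subjects will receive an IV administration of 100 µg/ 10 mCi Tc 99m tilmanocept". The third step doubles the mass and returns to 5 mCi, with 200 µg/5 mCi given twice, first SC and then IV about a week later. Planned numbers are 4, 4 and up to 6.

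Section 5.3 also sets the escalation rule. One ADR among four subjects adds two more at the same mass and the same radiolabel level. In the expanded cohort, no further ADR means escalation continues, one further ADR makes the current dose the MTD, and more than one makes the previous dose the MTD. The stop clause follows: "Dose escalation will continue until the MTD is found or until Cohort 3 is reached with only one ADR or without any ADRs". The next sentence is the definition: "The maximum tolerated dose is defined as the highest dose level at which no more than 33% of subjects experienced an ADR".

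Protocol 9.4 bases its expectation of no ADRs on a previous study at 200 µg/5 mCi, described as "i.e., the maximum dose planned for this study". SAP 1.3 makes the same argument in a nearly identical paragraph, but from a previous study at 400 µg/10 mCi, described as "i.e., twice the maximum dose planned for this study".

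Protocol section 9 names determination of the MTD as the statistical objective. SAP section 5.0 and Table 20 tabulate subjects with ADRs by cohort and overall. The SAP text supplied contains no MTD rule and no table that reports one.

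**The concern.** An MTD rule needs an ordered set of doses. Here dose has two components, and from Cohort 2 to Cohort 3 one doubles while the other halves. The definition, the stated planned maximum and the phrase about twice that maximum all assume a single scale that neither document sets out.

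The gap matters most in the outcome the plan itself expects. With no ADRs, the trial could report 200 µg/5 mCi as maximum tolerated although no dose exceeded the limit and another cohort had tolerated twice the activity. Because the SAP is silent, the answer to the stated statistical objective would be chosen after the data are seen. The prior exposure cited in support of the no-ADR expectation also differs between the two documents.

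**Working it through.** 1. **The plan's own figure.** Enrolment without expansion of Cohorts 1 and 2 is 4 + 4 + 6 = 14, as protocol 9.4 and SAP 1.3 state. It is a sum of cohort sizes; no power calculation is involved.

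2. **Ordering the doses** (protocol 5.2, Table 1).

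| | Mass (µg) | Activity (mCi) |
|---|---|---|
| Cohort 1 | 100 | 5 |
| Cohort 2 | 100 | 10 |
| Cohort 3, each injection | 200 | 5 |
| Cohort 3, SC + IV total | 200 + 200 = 400 | 5 + 5 = 10 |

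Per injection, the order by mass is C1 = C2 < C3 and by activity C1 = C3 < C2. Cohorts 2 and 3 cannot be ranked on both components. On cumulative administered dose, neither component falls from one cohort to the next.

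3. **The stated maxima.**
- Protocol 9.4's dose against Cohort 2: mass 200/100 = 2.0, activity 5/10 = 0.5.
- SAP 1.3's dose against Cohort 2: mass 400/100 = 4.0, activity 10/10 = 1.0.
- SAP 1.3's dose against one Cohort 3 injection: mass 400/200 = 2.0, activity 10/5 = 2.0.

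Both descriptions therefore hold only if a single Cohort 3 injection is taken as the maximum. Neither holds for Cohort 2's activity.

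4. **The no-ADR outcome.** Every cohort shows 0%, within the limit. The definition then gives Cohort 3 if ranked by mass or cohort number, and Cohort 2 if ranked by activity per injection. The stop clause places reaching Cohort 3 with no ADR, or with one, after the word or, beside the MTD being found. It can be read as an alternative to finding an MTD.

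5. **The 2-of-6 case.** One initial and one further ADR give 2/6 = 33.3%. Section 5.3 deems that dose the MTD, yet 33.3% is above a literal limit of 33%.

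6. **Precision of an ADR-free cohort.** The one-sided 95% exact upper bound with no events is 1 − 0.05^(1/n):
- n = 4: 1 − 0.05^(1/4) = 0.527
- n = 6: 1 − 0.05^(1/6) = 0.393

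**The case against.** Much can be said for the plan, and it limits the point.

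- **Order by sequence or cumulative exposure.** The previous dose plainly means the preceding cohort. The primary variable in protocol 9.2 covers the subject's whole participation, and over both injections Cohort 3 receives 400 µg/10 mCi, never below Cohort 2. This stands: an order is available. But protocol 2.1 speaks of escalating IV doses, and 9.4 names a single-injection dose as the maximum, so the basis still has to be stated.
- **Prior doses.** A reader might infer that the protocol and SAP cannot both be right about the supporting study, or that 10 mCi had no earlier support. The documents do not show either. Each refers only to a previous study, and protocol 1.3.4 lists IV dosing up to 400 µg and up to 10 mCi among 60 subjects, with no drug-related adverse reaction. It gives no counts per µg/mCi pair, so the two paragraphs remain unreconciled.
- **Stop clause.** A reader might infer that the protocol declares the MTD not found when Cohort 3 is free of ADRs. That rests on one conjunction. The clause may only mean stopping for toxicity or at the last planned cohort, and where 5.3 intends no MTD it says outright that none can be determined. The escalation diagram in Appendix 3 is not shown and may settle this; 5.3 points instead to Appendix 2, a schedule of events.
- **Upper bounds.** A reader might take 53% and 39% as breaching the 33% limit. They do not: the limit applies to the observed fraction. With no events the bound first falls below 33% at n = 8 (1 − 0.05^(1/8) = 0.312; at n = 7 it is 0.348), so no cohort of 4 or 6 could meet it.
- **Cohort 3 staying closed after Cohort 2 fails.** This follows from the sequential rule and is not a contradiction.
- **Primary endpoint.** The ADR proportion is properly tabulated, and no document makes a claim about 200 µg with 10 mCi in one injection. That stands, but it leaves the section 9 objective without an analysis.

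**Conclusion.** The point holds as a defect of definition and consistency. The plan does not state the basis for the highest dose level. Its stated maximum understates Cohort 2's activity by half, and the SAP's claim of twice the maximum is 1.0 times on that component. In the expected outcome the definition, read by mass or cohort order, labels 200 µg/5 mCi the MTD with no toxicity observed, and the SAP does not say what would be reported.

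This rests on reading dose per injection, as protocol 9.4 does, and on the text without the Appendix 3 diagram. It does not affect the ADR tabulation, and it takes no view on which dose order or escalation rule is right.

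**What to change.** - **Prior support.** Reconcile protocol 9.4 and SAP 1.3 to the supporting study or studies, with the number of subjects at each µg/mCi pair. State the planned per-injection maxima separately: 200 µg and 10 mCi.
- **MTD wording.** The sponsor should state what the highest dose level is ranked by, and reconcile the MTD definition, the stop clause and the 2-of-6 rule across protocol 5.3, protocol section 9 and the SAP. Correct the appendix reference in 5.3.
- **Reporting.** If no cohort's ADR fraction exceeds the limit and no expansion rule has named an MTD, report that no dose-limiting level was identified among the doses tested. Give the ADR count and exact upper bound per cohort for information, not as a test of the 33% rule.
- **Limits of the claim.** Make no statement about 200 µg with 10 mCi in one injection. Add a footnote to SAP Table 20 that Cohort 3 ADRs are counted over an SC and an IV injection. For that reason Cohort 1 against Cohort 3 is not a clean comparison of mass.

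The cost is wording in both documents and one table footnote. The downside is a more modest claim than an MTD. Dosing and enrolment do not change.

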5.4 Packaging and Labeling

Tilmanocept cartons ready for radiolabeling will be shipped and stored at the region-specific Cardinal Health radiopharmacy. Tilmanocept is provided in a vial. Vials are packaged as a kit. A carton contains five vials of tilmanocept. One kit, which is one tilmanocept vial, should be used for no more than one subject. The carton also contains five shield labels and 25 syringe labels. This package has been designed specifically for tilmanocept and protects the vials during shipment, handling, and storage. Navidea will provide a radiolabeling protocol and Quality Control worksheets. Cardinal Health will radiolabel tilmanocept with the protocol cohort specified tilmanocept dose and the cohort assigned millicurie dose Tc 99m in 1.0 mL and deliver one syringe for IV doses and two syringes (0.5 mL each) for SC doses to the clinical site that is/are ready for administration.

5.5 Investigational Product Accountability

The investigator (or designated personnel) will confirm receipt of the investigational product in writing and will use the investigational product only within the framework of this clinical trial and in accordance with this study protocol. For each subject, he/she will keep a record of the investigational product dispensed and all other accompanying forms to the investigational product. These documents are to be filed in the ISF.

Overall drug accountability and reconciliation will be completed by the sponsor or its representative. A list of investigational product vials and other materials that were returned, or destroyed, must be recorded and signed by the principal investigator (PI) or an appropriately qualified designee as documented in the study site responsibility sheet. Each time the investigational product is dispensed to a subject, the following information should be recorded on the Drug Accountability Log: subject number, radiolabel date, and the date delivered to nuclear medicine. At the completion or termination of the trial, a final drug accountability review and reconciliation must be completed and any discrepancies must be investigated and their resolution documented. All unused trial kits will be destroyed in accordance with institutional destruction procedures.

6 THERAPIES OTHER THAN INVESTIGATIONAL PRODUCT

6.1 Prior and Concomitant Therapy

All medications taken 30 days prior to Visit 2 (Day 1) Tc 99m tilmanocept injection through the Follow-Up Phone Call will be documented.

6.2 Post-Study Therapy

There are no post-study therapy restrictions.

7 STUDY PROCEDURES

Cohorts 1, 2, and 3:

7.1 Screening Visit (within 30 days of Day 1 injection)

- Obtain signed informed consent for study participation
- Preliminary review of inclusion and exclusion criteria
- Allocation of unique subject number; this number will be used to document the subject data in the case report forms (CRFs) and enrollment log
- Interview including the following subject-specific characteristics:
 - Demographic data - date of birth, gender, race
 - Medical/surgical history - all relevant prior medical and surgical conditions will be recorded in the CRF. Documented medical conditions will also note the month and year of onset if the condition is still active.
 - Concomitant Medications (within 30 days before Day 1 injection).
- Vital signs (body temperature, heart rate, blood pressure, and respiratory rate after at least 1 minute in a resting position).
- Electrocardiogram (ECG); subjects will either have a normal ECG or an abnormal ECG deemed not clinically significant by the PI.
- Blood draw for routine hematology, chemistry, serum pregnancy test for women of child-bearing potential. Females of child bearing potential are defined as women that are not surgically sterile (hysterectomy or bilateral oophorectomy) nor postmenopausal for at least 1 year prior to screening. Women who are not of childbearing potential will not require a pregnancy test.
- Urine collection for routine urinalysis.
- Physical examinations will include assessment of height and weight and an examination of general appearance, skin, eyes, ears, nose, throat, head and neck (including thyroid), lungs, heart, abdomen, lymph nodes, musculoskeletal, and nervous system. Any clinically relevant finding is to be documented as a baseline finding. Physical exams that are conducted as standard of care prior to signing informed consent may be used if they are performed within 30 days of injection.
- Assessment of edema/lymphedema, utilizing a pitting edema scale as provided in [Appendix 3](#), will be performed.
- KS history and classification.
- KS Lesion Assessment:
 - Cutaneous KS evaluation: All cutaneous lesions will be identified, documented, and photographed during the screening exam. Photographs will be collected per the photography protocol currently in use within the Department of Dermatology at UCSF, as provided in [Appendix 4](#).
 - Non-cutaneous KS evaluation: Confirmed based on specific appropriate tests or suspected based on clinical symptomology. Non-cutaneous lesions will be identified and documented.

Changes in health occurring after consent and prior to the day of injection will be added to the subject's medical history unless related to a study procedure.

Cohorts 1 and 2:

7.2 Day 1 (IV Injection)

7.2.1 Before Injection

- Assessment of adverse events
- Concomitant medication review
- A negative urine pregnancy test for women of child-bearing potential within 48 hours of injection.
- Final check of inclusion/exclusion criteria
- Vital signs (body temperature, heart rate, systolic and diastolic blood pressure, and respiratory rate within 30 minutes prior to investigational product injection, after at least 1 minute in a resting position)

7.2.2 IV Administration of Tc 99m tilmanocept

IV administration of Tc 99m tilmanocept will be at study time 00:00. The preferred site of IV placement will be the left or right antecubital vein.

Tc 99m tilmanocept shall be administered through the catheter as a slow IV push followed by a 10 cc sterile normal saline flush. The injection will be performed in the nuclear medicine department by an onsite Certified Nuclear Medicine Technologist or Nuclear Medicine Physician.

7.2.3 Post-Injection

The following procedures will be completed at the specified timepoints:

- 0-30 Minutes Post-Injection
 - ECG (completed before vital signs)
 - Vital signs (body temperature, heart rate, systolic and diastolic blood pressure, and respiratory rate) will be collected
 - Assessment of adverse events
- 60-75 Minutes Post-Injection
 - Assessment of adverse events
 - Whole body planar imaging
 - Optional SPECT/CT region(s) of interest imaging
- After the 60-75 Minute Imaging:
 - Clinical labs and urinalysis will be performed.
 - A KS tissue biopsy will be taken of an imaging-visualized non-visceral lesion

- If no lesion is visualized on imaging, a lesion of at least 5-6 mm in a clinically accessible area will be biopsied as chosen by the Investigator(s) who will record selection and rationale
- A photograph of the biopsy site with a measurement scale must be taken and stored with the subject's research chart

7.3 Follow-Up Telephone Call (7±3 days after Tc 99m tilmanocept injection)

- Concomitant medication review
- Assessment of adverse events

Cohort 3:

7.4 Day 1 (SC Injection)

7.4.1 Before Injection

- Assessment of adverse events
- Concomitant medication review
- A negative urine pregnancy test for women of child-bearing potential within 48 hours of injection.
- Final check of inclusion/exclusion criteria
- Vital signs (body temperature, heart rate, systolic and diastolic blood pressure, and respiratory rate within 30 minutes prior to investigational product injection, after at least 1 minute in a resting position)

7.4.2 SC Administration of Tc 99m tilmanocept

SC administration of Tc 99m tilmanocept will be at study time 00:00. The preferred site of SC injection placement will be the ankle(s) or the dorsal surface of the foot (feet).

The injection will be performed in the nuclear medicine department by an onsite Certified Nuclear Medicine Technologist or Nuclear Medicine Physician.

7.4.3 Post-Injection

The following procedures will be completed at the specified timepoints:

- 0-30 Minutes Post-Injection
 - ECG (completed before vital signs)
 - Vital signs (body temperature, heart rate, systolic and diastolic blood pressure, and respiratory rate) will be collected
 - Assessment of adverse events
- 60-75 Minutes Post-Injection

- Assessment of adverse events
- Whole body planar imaging
- Optional SPECT/CT region(s) of interest imaging
- 4-6 Hours Post-Injection
 - Assessment of adverse events
 - Whole body planar imaging
 - Optional SPECT/CT region(s) of interest imaging
- After the 4 – 6 Hour Imaging:
 - Clinical labs and urinalysis will be performed.

7.5 Day 7 ± 3 (IV Injection)

7.5.1 Before Injection

- Follow-up assessment from SC injection including changes in concomitant medication and adverse events
- A negative urine pregnancy test for women of child-bearing potential within 48 hours of injection.
- Final check of inclusion/exclusion criteria
- Vital signs (body temperature, heart rate, systolic and diastolic blood pressure, and respiratory rate within 30 minutes prior to investigational product injection, after at least 1 minute in a resting position)

